7.4.1 Safety Criteria for Adjustment or Stopping Doses

7.4.1.1 SEL-212 or Placebo

A patient will be withdrawn from study drug for meeting the following stopping rule:

- sUA level < 2.0 mg/dL, measured 1 hour after the infusion of the second component of study drug is completed during Treatment Period 1
- AND
- sUA level > 1.0 mg/dL measured at the Day 21 visit of Treatment Period 1 or sUA level > 6.0 mg/dL at the Day 21 visit of any of Treatment Periods 2-11

Stopping rules will be assessed by an independent, central, unblinded medical monitor.

If withdrawn from study drug during the double-blind treatment period (Treatment Period 1 to 6) or the double-blind extension period (Treatment Period 7 to 12), regardless of reason, the patient will continue study visits to the end of Treatment Period 12.

The window for all Day 21 visits is +2/-1 days. If a Day 21 visit sUA value drawn within the protocol window is not available, but if a sUA value drawn at an unscheduled visit after the Day 21 window is available prior to dosing that is ≤ 1.0 mg/dL during Treatment Period 1 or ≤ 6.0 mg/dL during Treatment Periods 2-11, the patient will not be required to be withdrawn from study drug and will be eligible to receive their subsequent dose.

If 1) a Day 21 visit sUA value drawn within the protocol window is not available and no subsequent sUA results are available or 2) a Day 21 visit sUA value drawn within the protocol window is not available and

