a subsequent sUA drawn at an unscheduled visit after the Day 21 window is > 1.0 mg/dL during Treatment Period 1 or > 6.0 mg/dL during Treatment Periods 2-11, then the patient will be withdrawn from study drug based on the protocol deviation. If a protocol deviation occurs where a patient is not able to be dosed within the dosing day window (for example in the case of COVID-19 restrictions temporarily preventing dosing) the current treatment period will be extended up to a maximum of 90 days without skipping doses for patients with a Day 21 visit sUA value ≤ 1.0 mg/dL during Treatment Period 1 or ≤ 6.0 mg/dL during Treatment Periods 2-11 in the D21 visit window or subsequent up to the rescheduled dosing visit. If this protocol deviation occurs such that the patient was unable to be dosed within the dosing day window for the Treatment Period 7 Day 0 dose, then the Treatment Period 6 Day 28 visit should still occur 28 days (+3/-4 days) after the Treatment Period 6 dose or as close to the visit window as possible to collect the final primary endpoint sUA sample. In this specific instance, the dosing day Treatment Period 7 Day 0 should then occur as soon as possible afterward up to a maximum of 90 days from the preceding dose.

To maintain the blind, a central group of unblinded pre-specified medical personnel will adjudicate the implementation of the stopping rules.

If withdrawn from study drug, the patient will continue study visits to the end of Treatment Period 12. At the discretion of the Investigator, the patient will be permitted to return to ULT 60 days after the patient's last study drug treatment. ULT shall not be SEL-212 or any experimental or marketed uricase (e.g., rasburicase (Elitek, Fasturtec), pegloticase (Krystexxa®), for the remainder of the study.

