13.5.2 Adverse Events / Adverse Drug Reactions

All AEs will be coded and grouped into Preferred Terms (PT) by System Organ Class (SOC), using the most recent MedDRA Version. All AEs will be summarized by SOC and PT.

Summaries by each treatment group for the whole study (i.e., double-blind treatment phase and double-blind extension phase) and for the double-blind treatment phase will be provided on the Safety Set overall and by SOC and PT with the number and percentage of patients reporting TEAEs, serious TEAEs, treatment-related TEAEs, AEs of special interest (AESIs), infusion reactions (this is a study drug-related AE that occurs within 24 hours after initiation of study drug infusion), TEAEs leading to withdrawal and TEAEs leading to death. Additional analysis will be performed on a subset of infusion reactions (this is a study drug-related AE that occurs within 1 hour after completion of study drug infusion) that fulfil the criteria of an Allergic Reaction/Hypersensitivity according to the Rheumatology Common Toxicity Criteria, version 2.0. In the overall summary, additionally, the number and percentage of patients with at least one severe TEAE, with at least one moderate TEAE but no severe TEAE and with only mild TEAEs will be provided. Similar summaries will be produced for the subset of patients continued into the double-blind extension phase (i.e., on the EPS) considering the whole study but also separately for each treatment phase.

The number and percentage of patients with TEAEs / serious TEAEs / treatment-related TEAEs / TEAEs of special interest and TEAEs leading to withdrawal will be summarized by SOC and PT for each treatment group and overall for the whole study and for the double-blind treatment phase on the Safety Set. Similar summaries will be produced for the subset of patients continued into the double-blind extension phase (i.e., on the EPS) considering the whole study but, also separately for each treatment phase.

Event rates by treatment group and overall will be provided for patients with at least one related TEAE, at least one SAE, and at least one TEAE of special interest. Additionally, the rate difference with 95% confidence interval comparing each SEL-212 treatment group to placebo as well as comparing the integrated SEL-212 arms to placebo will be provided.

TEAEs will also be summarized by maximum intensity and relationship to study drug.

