### **10.1. Extent of Exposure**

Number and percentage of patients who received the first 6 cycles of study treatment (i.e., completed study treatment) of the double-blind treatment phase and who received only 5, 4, 3, 2, or 1 cycles will be presented by treatment group and overall. Additionally, the number and percentage of patients who received all 6 cycles of study treatment within the double-blind extension phase (TP7 to TP12) and who received only 11, 10, 9, 8, or 7 cycles will be presented by treatment group and overall for the EPS. The dose applied in each treatment period TP1 to 12 will be summarised by SEL-212 group.

Number and percentage of patients who met the stopping rules will be summarized by treatment group, overall SEL-212 and treatment period. The percentage will be plotted versus treatment period by treatment group for the treatment phase on the SS. Additionally, the percentage will be plotted versus treatment period by treatment group for the whole study (treatment phase and extension phase) on the EPS.

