### **10.3. Adverse Events / Adverse Drug Reactions**

All adverse events (AEs) will be coded using the most recent MedDRA Version. All AEs will be summarized by system organ class (SOC) and preferred term (PT) for each treatment group, for overall SEL-212 and in total for the whole study, but also for the double-blind treatment phase and the double-blind extension phase separately. A treatment-emergent AE (TEAE) is an AE that starts or worsens at any time after

This document is confidential.

initiation of study drug on Day 0 of Treatment Period 1 until the End of Study Visit (30 days after completion of the last dose of study drug). TEAEs will be further classified as treatment-emergent for the double-blind treatment phase (these are all AEs which start prior to the first dose in the extension phase) and as treatment-emergent for the double-blind extension phase (these are all AEs which start after the first dose in the extension phase or increase in intensity after start of study drug in the extension phase). Additional analysis will be performed on a subset of infusion reactions (this is a study drug-related AE that occurs within 1 hour after completion of study drug infusion) that fulfil the criteria of an Allergic Reaction/Hypersensitivity according to the Rheumatology Common Toxicity Criteria, version 2.0.

Following AEs are considered as AEs of special interest (AESIs): gout flares, infections, malignancies, viral infections, interstitial lung disease, stomatitis, infusion-related reactions including anaphylaxis, thrombosis (e.g., deep venous thrombosis, pulmonary embolism), and the following laboratory tests, if deemed clinically significant by the PI: hyperlipidemia, worsening of renal function tests, proteinuria, and leukopenia.

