An overall summary will be provided of the number and percentage of patients reporting AEs, TEAEs, treatment-related (possibly related and related) TEAEs, serious TEAEs, treatment-related serious TEAEs, AESIs, infusion reactions (this is a study drug-related AE that occurs within 24 hours after initiation of study drug infusion), infusion reactions (this is a study drug-related AE that occurs within 1 hour after completion of study drug infusion) that fulfil the criteria of an Allergic Reaction/Hypersensitivity according to the Rheumatology Common Toxicity Criteria, version 2.0. Any gout flare which occurs within 24 hours after initiation of study drug infusion will be listed as a gout flare and not as an infusion reaction. TEAEs leading to study drug withdrawal and TEAEs leading to death. In the overall summary, additionally, the number and percentage of patients with at least one severe TEAE, with at least one moderate TEAE but no severe TEAE and with only mild TEAEs will be provided. The overall summary will be provided for all AEs in the study and for the AEs in the double-blind treatment phase on SS. Additionally, the overall summary will be provided for the whole study and for each period on EPS.

The number and percentage of patients with TEAEs / treatment-related TEAEs / serious TEAEs / AESIs / TEAEs leading to study drug withdrawal/ will be summarized by SOC and PT for each treatment group. TEAEs will also be summarized by SOC and PT for maximum intensity and maximum causality for each treatment group. All defined summaries will be provided for all TEAEs in the study and for the TEAEs in the double-blind treatment phase on SS. Additionally above defined summaries will be provided on the EPS for the whole study and for each period.

Exposure-adjusted event rates based on i) patients and also based on ii) events by treatment group, overall SEL-212 and total will be provided for patients with at least one related TEAE, at least one SAE, at least one TEAE of special interest and also for specific TEAEs of special interest. For SAEs and AESIs that occur in  $\geq 2\%$  of individuals, as well as the most common TEAEs, the rate difference of exposure-adjusted event rates between the two treatment groups together with the 95% confidence interval will be provided; this will also be presented for the two treatment groups combined vs. placebo.

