i) Exposure –adjusted event rate in treatment group A based on patients = Number of all patients with at least one event in treatment group A / Total sum of the treatment exposure time of all patients in treatment group A.

ii) Exposure –adjusted event rate in treatment group A based on events = Number of all events in treatment group A / Total sum of the treatment exposure time of all patients in treatment group A.

This document is confidential.

Listings of TEAEs and non-TEAEs will be provided. The treatment-emergent AEs for the double-blind treatment phase and for the double-blind extension phase will be flagged, respectively.

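### SAP 10.3 patient-based exposure-adjusted rate keeps time after the first event in its denominator, which distorts comparisons for common adverse events (minor)

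*SAP*

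**What the plan says.** SAP 10.3 plans two exposure-adjusted rates. Rate (i) is "Number of all patients with at least one event in treatment group A / Total sum of the treatment exposure time of all patients" in that group; rate (ii) puts all events over the same denominator. They are given for related TEAEs, SAEs and AESIs. For SAEs and AESIs in at least 2% of patients and for the most common TEAEs, "the rate difference of exposure-adjusted event rates between the two treatment groups together with the 95% confidence interval will be provided", and the two SEL-212 groups combined are also set against placebo. Protocol 13.5.2 asks for "the rate difference with 95% confidence interval comparing each SEL-212 treatment group to placebo as well as comparing the integrated SEL-212 arms to placebo", but speaks of event rates without saying that they are exposure-adjusted.

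Exposure time is not defined. SAP 10.1 counts cycles ("Number and percentage of patients who received the first 6 cycles of study treatment") and doses, and SAP 10.2 gives volumes and infusion durations. TEAEs run from the first dose "until the End of Study Visit (30 days after completion of the last dose of study drug"); the treatment-phase class is then "these are all AEs which start prior to the first dose in the extension phase".

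The stopping rule in Protocol 7.4.1.1 requires "sUA level < 2.0 mg/dL, measured 1 hour after the infusion of the second component of study drug is completed during Treatment Period 1" together with a high Day 21 value. Patients withdrawn from drug stay on study visits to the end of Treatment Period 12.

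**The concern.** A patient who has had a first event can no longer add to the numerator of rate (i), yet that patient's later time still enlarges the denominator. The result is a proportion divided by mean exposure, so it depends on how long the group was exposed even when the underlying hazard is the same.

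Exposure will differ by arm. Patients enter with sUA of at least 7 mg/dL, and saline will hardly bring the 1-hour value below 2.0 mg/dL, so the sUA stopping rule acts almost only on SEL-212. Placebo patients can still be withdrawn for other reasons: with no usable Day 21 value, "then the patient will be withdrawn from study drug based on the protocol deviation".

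These rates are the plan's adjustment for unequal time on drug. For common events, rate (i) can show a difference that is not there or shrink one that is.

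**Working it through.** The documents give no exposure-adjusted rate to reproduce, so this is a model check.

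**Inputs.** Treatment phase T = 168 days (SAP 3.3). A fraction p of SEL-212 stops after Treatment Period 1 (t = 28 days), with p = 0.30 or 0.55. This is an assumption, set near two figures: 61-71% kept sUA control at week 12 in Phase 2 Part C (Protocol 7.6.3.2.1), and 45% responders are assumed (Protocol 13.1). No placebo stops; 40 patients per arm. Constant hazard L per year of 365.25 days. L = 7 is an upper case: Protocol 5.4 gives it as a background flare rate, and Protocol 10.6.1 provides flare prophylaxis.

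**Rate (i).**
- Placebo = (1 - exp(-LT)) / T.
- SEL-212 = [(1-p)(1 - exp(-LT)) + p(1 - exp(-Lt))] / [(1-p)T + pt].
- Mean SEL-212 exposure: 0.70 × 168 + 0.30 × 28 = 126 days (0.345 years), or 0.45 × 168 + 0.55 × 28 = 91 days (0.249 years). Placebo: 168 days (0.460 years).
- Example, L = 2, p = 0.55: SEL-212 0.3488/0.2491 = 1.400; placebo 0.6014/0.4600 = 1.308; ratio 1.07. Both are well below the true 2.

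**Equal hazards (true ratio 1).** The 95% CI half-width is 1.96 × sqrt(r1/PT1 + r2/PT2), where r is the rate and PT the person-time in each arm. This Poisson form is assumed, because the SAP names no method.

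| L per year | Placebo (i) | SEL-212 (i) | Ratio | Difference | Share of half-width |
|---|---|---|---|---|---|
| 0.5 | 0.447 | 0.450-0.454 | 1.01-1.02 | 0.003-0.007 | about 1% |
| 2 | 1.308 | 1.344-1.400 | 1.03-1.07 | 0.036-0.093 | 5-10% |
| 7 | 2.087 | 2.309-2.651 | 1.11-1.27 | 0.222-0.564 | 21-47% |

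At 0.1 per year the ratio is 1.001-1.003.

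Sensitivity at 2 and 7 per year:
- Stops after Treatment Period 2 or 3 instead: 1.04-1.09 and 1.12-1.31.
- 10% of placebo also stopped after Treatment Period 1: 1.02-1.06 and 1.08-1.23.
- Both phases (12 doses on placebo, window to last dose + 30 days, 55% of SEL-212 stopped within Treatment Periods 1-5): 1.10-1.16 and 1.39-1.47.

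**True ratio 2.** Same formulas, with hazard 2L on SEL-212:
- 1 v 2 per year: 1.344-1.400 against 0.802, ratio 1.68-1.75.
- 2 v 4 per year: 1.937-2.102 against 1.308, ratio 1.48-1.61.

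The real excess is compressed.

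**Rate (ii), equal hazards.** It has no first-event problem, so only the choice of exposure time matters. Count events to 168 days in completers and to last dose + 30 days in stopped patients. The mean event window on SEL-212 is 0.70 × 168 + 0.30 × 30 = 126.6 days, or 0.45 × 168 + 0.55 × 30 = 92.1 days.
- Exposure = 28 days × doses: 126.6/126 = 1.005; 92.1/91 = 1.012.
- Exposure = first to last dose (completers 140 days, stopped patients 0): (126.6/98)/(168/140) = 1.08; (92.1/63)/(168/140) = 1.22.
- Exposure = study time: 126.6/168 = 0.75; 92.1/168 = 0.55.
- Stops after Treatment Period 3 instead: 1.04-1.09 and 0.73-0.85 for the last two.
- Exposure = event window: 1.00.

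**Limit of the remedy.** Under constant hazard, events over time to first event returns L in each arm. Now let the hazard fall equally in both arms, from an assumed 4 per year in the first 28 days to 2 or 1 per year. Time to first event still gives 1.06-1.30, and rate (ii) with matched windows gives 1.05-1.28.

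**The case against.** Four counter-arguments carry weight.

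1. A reader might infer that rate (i) is simply tilted against SEL-212. That follows only when hazards are equal. With a true SEL-212 excess the formula works the other way and hides part of it. The documents do not settle which case applies.

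2. A reader might infer that the undefined exposure time leaves both rates open to large bias. The natural reading is 28 days per dose with TEAEs to 30 days after the last dose, and the error is then about 1%. The large figures need exposure to be programmed as first-to-last dose, which gives a dosed patient zero exposure, or as study time, which does not fit the SAP's term. The event window is also largely settled. SAP 10.3, Protocol 12.2.1.1 and 12.2.3.1, and Appendix A footnote 1 agree on about 30 days after the last dose; only the End of Study visit timing in Protocol 7.1.3 differs. For a patient with no extension dose, the 30-day limit applies first and all TEAEs fall in the treatment phase.

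3. The large rate (i) case is flares. They are also analysed as key secondary endpoints per length of observation (SAP 9.3.2.8 and 9.3.2.9), without the first-event problem. Counts, percentages and rate (ii) stand beside rate (i).

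4. Protocol 7.6.3.2.2 says that TEAEs in Phase 2 were most frequent after the first cycle and then diminished. The remedy is therefore not exact, and the residual can exceed the distortion removed at 2 per year.

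All four stand as limits on size and direction. None justifies the stated formula: it mixes a first-event count with time that is not at risk of a first event.

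**Conclusion.** The point holds, as a minor one. Rate (i) in SAP 10.3 understates the rate of common events. The amount depends on event frequency and exposure length, and exposure length will differ by arm. Under the assumptions above, the false ratio is at most 1.02 at 0.5 per year, 1.03-1.07 at 2 per year and 1.11-1.27 in the upper case of 7 per year; a true ratio of 2 reads as 1.48-1.75. The effect is negligible for rare SAEs.

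The undefined exposure time is a matter of clarification, not a demonstrated bias. The figures rest on constant hazards and on assumed stopping patterns. The outputs are descriptive, and no confirmatory test is touched.

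**What to change.** In SAP 10.3:
- For rate (i), replace the denominator with each patient's time from first dose to first event, or to the end of the TEAE window if there is no event.
- State that exposure time is the window in which events are counted: first dose to last dose + 30 days for TEAEs, ending for the treatment phase at the first extension dose if one is given. Rate (ii) uses that whole window. Name the window for the SAE rate as well.
- Add one sentence saying that, if events concentrate in the first cycle, unequal exposure leaves some imbalance in both rates.

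In the protocol, reconcile the End of Study timing in 7.1.3 with the 30-day window for patients who stop drug early.

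The cost is one formula, one definition and a wording change. Dosing and event dates are already collected.

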#### **10.4. Laboratory Evaluations**

Laboratory data will be presented in separate tables for each laboratory test type (hematology, blood chemistry, coagulation, antibodies, lipids). Each laboratory parameter will be summarized by scheduled visit – including visits of the extension phase - and by treatment group, overall SEL-212 and total, presenting actual values and change from baseline. The values from unscheduled visits will be included in analyses according to the rules set out in Section 7.4. For the TP 7 to 12 of the extension phase additionally the change from baseline of the extension phase (D0 TP7) will be summarized. Shift tables of the number and percentage of patients below normal range (low), within normal range (normal) and above normal range (high) at each scheduled post-baseline visit of the double-blind treatment period compared to the low/normal/high categorization at baseline will be provided by treatment group on SS. Shift tables of the number and percentage of patients below normal range (low), within normal range (normal) and above normal range (high) at each scheduled visit of the double-blind treatment and the extension period compared to the low/normal/high categorization at baseline and for visits of the extension period additionally at baseline of the extension period (Day 0 TP7) will be provided by treatment group on EPS. A listing of clinically significant abnormal values in the whole study but also separately for the treatment and the extension phase will be provided in the tables section on SS and EPS, as appropriate. Biomarkers and multiomic markers assessed during the double-blind treatment phase will be summarized by treatment group on SS. Biomarkers assessed during the double-blind extension phase will be summarized by treatment on EPS. Pregnancy test results and drug screen results during the double-blind treatment phase and the extension phase will be listed on the SS, only.

#### **10.5. Vital Signs and Weight**

Summary tables of the actual values and changes from baseline will be provided for each vital sign parameter and weight at each scheduled visit - including visits of the extension phase - by treatment group, overall SEL-212 and total on SS. For the TP 7 to 12 of the extension phase additionally the change from baseline of the extension phase (D0 of TP7) will be provided.

#### **10.6. ECG**

For each 12-lead ECG variable the actual value and the change from baseline will be summarized for the scheduled visits - including visits of the extension phase - by treatment group, overall SEL-212 and total on SS. For the TP 7 to 12 of the extension phase additionally the change from baseline of the extension phase (D0 of TP7) will be provided.

A shift table of the number and percentage of patients with normal and abnormal and clinically significant abnormal values at each scheduled post-baseline visit of the double-blind treatment period compared to the normal / abnormal / clinically significant abnormal categorization at baseline will be provided by treatment group for the overall interpretation on SS. A shift table of the number and percentage of patients with normal and abnormal and clinically significant abnormal values at each scheduled visit of the double-blind treatment and extension period compared to the normal / abnormal / clinically significant abnormal categorization at baseline of the study will be provided by treatment group for the overall interpretation on EPS. Additionally, the shift of the extension period assessments compared to the baseline of the extension period will be provided on EPS. A frequency table with number and percentage of patients with abnormal

*This document is confidential.*

